#### 9.4.3 Safety

In general, safety data will be reported according to treatment initially received – i.e. RXC004

monotherapy or RXC004 + nivolumab combination. In order to explore any difference in the subjects who just received monotherapy compared to those who receive combination after progressing at the 8-week scan some safety data presentations will split the RXC004 into two groups – the monotherapy only subjects and the monotherapy followed by combination subjects as well as presenting them together. The tables that will be produced this way will be detailed in the SAP.

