2 STUDY OBJECTIVES

Objectives	Endpoints
Primary	
To assess the anti-tumour activity of RXC004 monotherapy and RXC004 + Nivolumab	Monotherapy: Disease control rate (DCR) using each patients Best Overall Response (BOR) according to RECIST 1.1 Combination: Objective response rate (ORR) using each patients BOR according to RECIST 1.1
Secondary	
To further assess the preliminary efficacy of RXC004 monotherapy and RXC004 + Nivolumab	% change in the sum of target lesions, duration of response (DoR), PFS, ORR (monotherapy) and DCR (combination) using investigator assessments according to RECIST 1.1 and OS
To assess the PK of RXC004 in monotherapy and in combination with Nivolumab	Maximum plasma concentration (Cmax) after Dose 1, Cmax at steady state, minimum observed plasma concentration (Cmin) at steady state as well as other relevant parameters (e.g. tmax, t ^{1/2} , λz, AUC _{0-∞} , CL/F, and Vz/F)
To assess the safety and tolerability profile of RXC004 monotherapy and RXC004 + Nivolumab combination	Incidence of AEs SAEs, dose reductions, interruptions and discontinuation and assessment of dysgeusia
Exploratory	
CCI CCI CCI CCI CCI	CCI CCI CCI CCI CCI CCI CCI CCI

CCI	CCI

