4.2.3 Definition of Baseline and Post-baseline Assessments

A baseline assessment will be defined as the last assessment performed prior to the first dose of study treatment (C0D1). While many of these assessments will be performed on the day of the first dose, others will be performed during screening. If a patient is missing an assessment typically performed on the day of the first dose, screening values may be substituted as baseline.

Patients treated with RXC004 monotherapy (arm A) that radiologically progress as per RECIST1.1 at the first 'on treatment' scan, may be treated with RXC004 + Nivolumab combination. Accordingly, the following groups of analyses have to be defined to clarify which patients and which information in arm A will be utilized:

- **Arm A (RXC004 monotherapy):** this group will include information for all patients enrolled in arm A.
- **Arm A1 (RXC004 monotherapy):** this group will include information of all patients enrolled in Arm A who were on monotherapy throughout the study - ie. subjects who did not radiologically progressed at the first scan (week 8) or who radiologically progressed

at the first scan (week 8) but remained on monotherapy or who withdrew before the first scan.

- **Arm A2 (RXC004 + Nivolumab):** this group will include information of patients enrolled in arm A who radiologically progressed at the first scan (Week 8) and then switch to receive combination therapy of RXC004 + Nivolumab either at Week 8 or later. The last scan before the switch to combination treatment will be set as the arm A2 baseline RECIST1.1 scan for the combination treatment. The date of the last scan before switching to combination treatment will also be used to determine the arm A2 baseline date for all the efficacy endpoints except OS. OS will keep the same baseline regardless of the progression. For assessments other than efficacy, Arm A2 summaries, will include data from start of monotherapy until end of combination treatment.
- **Arm B (RXC004 + Nivolumab):** this group will include information on all patients enrolled in arm B.

Some patients with symptomatically stable disease may continue treatment after the initial RECIST 1.1 - defined progression, until symptomatic/clinical progression or a second RECIST 1.1 PD assessment (relative to the initial RECIST1.1 progression, for a given study treatment).

Change from baseline is derived where both baseline and post-baseline values are available:

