Listing of all AEs (including non-treatment-emergent events) will be provided. This listing will be presented, ordered by arm and patient. It will include patient identifier, AE (SOC, PT, and verbatim term), date of onset, date of resolution, duration, maximum grade, seriousness, action taken, outcome and causality. A listing detailing the serious TEAEs will also be produced.

TEAEs summaries will be conducted for arm A and arm B and separately for arm A1 and arm A2 (in the same table) as applicable.

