4.12.3 Clinical Laboratory Evaluation

Blood samples for determination of clinical chemistry and haematology will be taken at the visits indicated in the SoA (see protocol). Additional safety samples may be collected if clinically indicated at the discretion of the investigator. The date, time of collection and results (values, units and reference ranges) will be recorded on the eCRF.

The clinical chemistry and haematology will be performed at a local laboratory at or near to the investigator site. Sample tubes and sample sizes may vary depending on laboratory method used and routine practice at the site.

In case of BLQ values (eg “<5”, “<100”) for some assessments, the following rule will be considered:

- If less than 50% of the assessments (across patients) are BLQ such as “<XXX”, then “XXX/2” will be considered for summaries.

- If 50% or more than 50% of assessments (across patients) are BLQ such as “<XXX” then “0” will be considered for summaries.

The following laboratory variables will be measured:

- Haematology (whole blood): Haemoglobin (Hb), Lymphocytes (absolute count and %), Neutrophils (absolute count and %), Platelet count, Total white cell count. . .
- Clinical Chemistry (serum or plasma): Albumin, Alanine transaminase (ALT), Alkaline phosphatase (ALP), Amylase (only for arm B), Aspartate transaminase (AST), Calcium, Calcium corrected, Creatinine, CRP, Glucose, Lactate dehydrogenase (LDH), Lipase (only for arm B), Magnesium, Phosphate, Potassium, Sodium, Total bilirubin, Urea. . .

The original lab test units will be converted using the International System of Units (SI) [11].

Laboratory test with numerical grading criteria in the NCI CTCAE v5.0 will be graded accordingly. Grade 0 will be assigned for all non-missing values not graded as 1 or higher. For laboratory tests where grades are not defined by CTCAE v5.0 results will be classified as low, normal or high based on laboratory normal ranges.

The following summaries will be provided for all parameters for arm A and arm B:

- A summary of results by assessment visit (as per SoA)
- Shift tables will be provided for all parameters to compare a patient’s baseline laboratory grade relative to worst post-baseline grade (Low and/or High abnormal direction will be considered for each parameter).

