6.2 Summary of treatment arms to be considered for each endpoint

Endpoints	Arms to consider
DCR	Arm A/B and arm A2
ORR	Arm A/B and arm A2
PFS	Arm A/B and arm A2
Percentage change in tumor size	Arm A/B and Arm A2
AEs	Arm A/B and Arm A1/A2
Rest of endpoints	Arm A/B unless otherwise specified

Approval Signatures

Document Name: Statistical Analysis Plan 30 May 2024 RXC004/0002

Document Number: VV-TMF-6954693

Parexel Version Number:

System Version Number: 1 .0

Document Approvals		
Reason for signing: Approved	Name: PPD	Role: PPD
		Date of signature: 28-May-2024 07:34:50 GMT+0000
Reason for signing: Approved	Name: PPD	Role: PPD
		Date of signature: 28-May-2024 09:38:11 GMT+0000
Reason for signing: Approved	Name: PPD	Role: PPD
		Date of signature: 30-May-2024 10:22:50 GMT+0000
Reason for signing: Approved	Name: PPD	Role: PPD
		Date of signature: 30-May-2024 10:57:28 GMT+0000

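### No planned safety table isolates the monotherapy period of all Arm A patients, or the post-switch period of those who cross over to the combination

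*SAP*

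**What the plan says.** SAP 4.2.3 defines four groups for presentation.

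- Arm A, headed as RXC004 monotherapy: "this group will include information for all patients enrolled in arm A". No cut at the switch is stated for safety data.
- A1, under the same heading: Arm A patients who never received the combination.
- A2, headed as RXC004 + nivolumab: Arm A patients who progressed at the week-8 scan and then crossed over. For these, "For assessments other than efficacy, Arm A2 summaries, will include data from start of monotherapy until end of combination treatment".
- Arm B: patients enrolled to the combination.

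The grouping follows Protocol 9.4.3: "In general, safety data will be reported according to treatment initially received". That section adds that some presentations will split Arm A by type of patient (monotherapy only, or monotherapy and then combination) and will also show the two together.

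For adverse events, SAP 4.12.1 says: "TEAEs summaries will be conducted for arm A and arm B and separately for arm A1 and arm A2". For laboratory data, SAP 4.12.3 says: "The following summaries will be provided for all parameters for arm A and arm B". Its shift tables set "baseline laboratory grade relative to worst post-baseline grade". SAP 6.2 assigns endpoints that it does not name, laboratory data among them, to "Arm A/B unless otherwise specified". The eDISH plots in SAP 4.12.3 have no stated grouping or cut.

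**The concern.** One secondary objective is "To assess the safety and tolerability profile of RXC004 monotherapy and RXC004 + Nivolumab combination". The switch adds nivolumab and, in the Arm A schedule (Protocol Table 1), changes the scheduled RXC004 dose from 2 mg to 1.5 mg once daily. The two periods are therefore different treatments. Protocol 2.3.1.2 names colitis as a possible overlapping toxicity, and Protocol 4.4.1.2 reports that the only drug-induced liver injury in Phase 1 was on the combination.

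If patients switch, an event or laboratory value arising after nivolumab can appear under a heading that reads as monotherapy, and an event on monotherapy can appear under one that reads as combination. The planned tables would give neither the monotherapy-period incidence for all of Arm A nor the combination-period incidence for switchers.

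**Working it through.** The plan gives no figure on this point, so there is none to reproduce. The check is a comparison of definitions, followed by two calculations of size.

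**1. What each column holds (SAP 4.2.3, 4.12.1, 6.2; Protocol 9.4.3)**

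| Column | SAP label | Patients | Periods in the safety data |
|---|---|---|---|
| A | RXC004 monotherapy | all Arm A | monotherapy plus switchers' combination period (inferred) |
| A1 | RXC004 monotherapy | non-switchers | monotherapy only |
| A2 | RXC004 + nivolumab | switchers | both (stated) |
| B | RXC004 + nivolumab | Arm B | combination arm, no switch |

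The entry for A is an inference from three facts: all Arm A patients' information is included, no safety cut is stated, and the protocol reports by initial treatment and shows the subgroups together. By contrast, the SAP does handle the switch elsewhere. Switchers count as progressed in Arm A for DCR, ORR and PFS (4.11.2.1, 4.11.2.2, 4.11.3.2), and the combination dose intensity is counted from the start of combination (4.10.1).

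**2. Laboratory data.** Arm A shifts run from the value before Cycle 0 Day 1 to the worst grade afterwards, so they pool the periods in the same way. By-visit output is unclear. It follows the schedule of assessments, which has separate combination columns, and SAP 4.2.1 restarts the day count at the switch. The windows in SAP 4.2.2 are relative to Cycle 1 Day 1 without saying which one.

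**3. Time pooled per switcher.** Inputs: qualifying scan at week 8 ± 1 and combination start within 28 days of it (Protocol 5.1, criteria 11 and 12); possible confirming scan at week 16 ± 1 (Appendix D, Figure 4 note); nivolumab every 4 weeks; treatment-emergent window to 90 days after the last nivolumab dose (SAP 4.12.1).

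- Monotherapy before the switch: earliest 7 × 7 = 49 days; latest direct switch 9 × 7 + 28 = 91; after a week-17 scan 17 × 7 + 28 = 147.
- Post-switch window after k doses: 28(k − 1) + 90, which is 90, 118 and 146 days for k = 1, 2 and 3.
- Post-switch share of the window = post / (post + mono):

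| Post-switch follow-up | mono 49 | mono 91 | mono 147 |
|---|---|---|---|
| k = 1 (90 days) | 90/139 = 64.7% | 90/181 = 49.7% | 90/237 = 38.0% |
| k = 3 (146 days) | 146/195 = 74.9% | 146/237 = 61.6% | 146/293 = 49.8% |
| stops at 30 days | 30/79 = 38.0% | 30/121 = 24.8% | 30/177 = 16.9% |

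These are calendar days including the safety tail, not shares of exposure or of events.

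**4. Effect on a rate (illustration only).** Take related Grade ≥3 events from Phase 1: 1/6 on 2 mg monotherapy (Protocol Table 5) and 3/8 on 1.5 mg with nivolumab (Table 9). Assume independent periods and a fraction f of switchers, which the documents do not give. Then Arm A column = 1/6 + f × (5/6) × q.

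| q | f = 10% | f = 25% | f = 50% |
|---|---|---|---|
| 3/8 | 19.8% | 24.5% | 32.3% |
| 2/8 (without the anaemia case with missing causality) | 18.8% | 21.9% | 27.1% |
| 2/7 (1.5 mg monotherapy, Table 5) | 19.0% | 22.6% | 28.6% |

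The starting value is 16.7%. Clopper-Pearson 90% intervals for the inputs are 0.9–58.2% (1/6), 11.1–71.1% (3/8), 4.6–60.0% (2/8) and 5.3–65.9% (2/7). The Table 9 note also gives a 30-day event tail rather than 90.

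**5. Treatment-emergent window (separate).** On one reading of SAP 4.12.1 and Protocol 9.4.3.1, the window for combination patients closes 90 days after the last nivolumab dose. Protocol Table 14 lets RXC004 continue alone. Example: last nivolumab on day 57 and RXC004 to day 200 leaves 200 − (57 + 90) = 53 on-drug days uncounted. The loss is zero unless RXC004 outlasts nivolumab by more than 90 days.

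**The case against.** The grouping is pre-specified and disclosed in Protocol 9.4.3, and the SAP implements it. A reader might infer that the two documents conflict; they do not. A reader might also infer that neither treatment's safety profile can be read from the tables. That goes too far: Arm B gives a combination column without a switch, and A1 gives nivolumab-free data. What is missing is narrower, namely the switchers' monotherapy time (and so the all-Arm-A monotherapy rate) and their post-switch rate.

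There are mitigations. Listings flag switchers (SAP 4.2.5) and carry onset dates (4.12.1), and the swimmer plot colours the two periods differently (4.10.1). In Arm A, nivolumab-related rows can reflect only events after the switch. These let a reader rebuild part of the split by hand, but none gives a period-specific incidence or shift. An RXC004-related event after the switch still sits in Arm A's RXC004-related row.

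It is also fair that the group labels are not table shells, and that A2's definition stands beside its label. Switching requires week-8 progression, combination eligibility and sponsor approval, so 20 (Protocol Table 1, footnote j) is a ceiling and not a forecast.

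Finally, cutting at the switch has its own cost. Delayed RXC004 toxicity would be booked to the combination; Protocol 2.3.1.2 describes Phase 1 colitis presenting in Cycle 2. This objection stands, and the remedy has to deal with it.

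**Conclusion.** The point holds as a minor-to-moderate reporting gap confined to patients who switch. That A2 spans both periods is stated outright. That Arm A does so is a firm inference. Pooling of Arm A worst-grade laboratory shifts follows from it. By-visit laboratory output and eDISH are unclear rather than shown to be pooled.

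The size depends on the number of switchers, which the documents do not give, and is nil if there are none. Per switcher, A2 includes 49 to 91 days of monotherapy, or up to 147.

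A reader might take the Phase 1 illustration as evidence that nivolumab raises event rates, or as a forecast for Arm A. It is neither. Putting in the 1.5 mg monotherapy rate moves the column by a similar amount, the intervals are very wide, and the switch fractions are assumed. It shows only that adding a second risk period raises a cumulative incidence.

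A reader might likewise infer that the treatment-emergent definition certainly drops events. The wording can also be read so that the closing limit applies only to pre-existing events that worsen, or so that a patient continuing RXC004 alone falls under the monotherapy limb. It needs clarifying, as a separate minor matter.

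**What to change.** Keep every table that Protocol 9.4.3 calls for, and change the SAP as follows.

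- **Labels (4.2.3).** Call Arm A the initial monotherapy arm, including post-switch data. Call A2 monotherapy followed by combination, which matches the protocol's own description.
- **Period flag (4.2.3, 4.12.1, 4.12.3).** Derive it at the first combination dose, where SAP 4.2.1 already restarts the day count and 4.10.1 already cuts dose intensity.
- **Added outputs.** Show treatment-emergent events, worst-grade laboratory shifts and eDISH for the Arm A monotherapy period, the A2 combination period and Arm B. Give patient-time beside the counts, since period lengths differ.
- **Baseline.** For combination-period laboratory shifts, use the last value before the first combination dose. Protocol Table 1 already schedules a draw before the first combination cycle.
- **Assignment and carry-over.** Place each event in the period of its onset or of its worsening in grade; grade changes are collected. State carry-over of delayed RXC004 toxicity as a limitation, and flag RXC004-related events that start within 30 days after the switch, or show them in a sensitivity table.
- **Separate minor change.** State that for combination patients the treatment-emergent window ends at the later of last nivolumab + 90 days and last RXC004 + 30 days. No change to event collection in Protocol 8.3.1 is clearly needed, since collection already runs throughout treatment.

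The cost is SAP wording, one derived variable and a few tables with small denominators, with some carry-over misattribution remaining. No new data are needed. The window clarification should be mirrored in Protocol 9.4.3.1.

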4.2.4 End of Study (EoS)

A participant is considered to have completed the study if he/she has completed all phases of the study (including the last visit and the last scheduled assessment shown in the SoA) or withdraws consent whichever occurs first.

The end of the study is defined as the date of the last visit of the last participant in the study or the last scheduled assessment shown in the SoA for the last participant in the study before the data cut off (DCO).

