## 7 DISCONTINUATION OF STUDY TREATMENT AND PARTICIPANT DISCONTINUATION/WITHDRAWAL

### 7.1 Discontinuation of Study Treatment

An individual patient will not receive any further IP (RXC004 or nivolumab) if any of the following occur;

- Patient decision to withdraw from further treatment with IP. The patient is, at any time,

free to discontinue treatment, without prejudice to further treatment

- Clinical or RECIST 1.1-defined radiological progression (symptomatically/clinically stable patients may continue treatment until symptomatic/clinical progression or second RECIST 1.1 progression [relative to the first 'on study treatment' RECIST 1.1 progression]). See Section 7.1.1 for details for continuing study treatment after RECIST1.1 defined progression
- An AE that meets discontinuation criteria in Appendix G or Table 14
- Pregnancy or intent to become pregnant
- Initiation of alternative anticancer therapy including another investigational agent
- Non-compliance with the study protocol that, in the opinion of the Investigator or Sponsor, warrants withdrawal from treatment with IP

Discontinuation from study treatment is NOT the same thing as a withdrawal from the study. If study treatment is permanently discontinued, the participant will remain in the study to be evaluated for safety, progression (if the patient discontinues for a reason other than progression) and survival. See the SoA for data to be collected at the time of discontinuation of study treatment and during follow-up.

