##### **9.4.1.1 Patient Disposition**

Patient disposition will be presented together with withdrawals from treatments, withdrawals from the study, and the reason for withdrawal.

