4.4 Study Patients

4.4.1 Disposition of Patients

A clear accounting of the disposition of all patients who enter the study will be provided from screening to study completion.

The number of patients who were screened (who signed main study ICF), were exposed to study treatment, who completed the study or discontinued and primary reason for end of treatment will be summarized for arm A and arm B in the FAS. The number of patients in arm A who switch from monotherapy to combination therapy will also be summarized. The number of patients in arm A and arm B who remained on original treatment despite disease progression will also be presented.

The patient disposition including the date the informed consent was signed, date of first/last intake of study drug and the primary reason for End of Treatment will be listed.

A listing of patients included into each of the analysis set will be presented, related summary statistics will be provided. Patients who did not meet the eligibility criteria or were screen failures will also be listed.

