4.15 Changes in the Conduct of the Study or Planned Analysis

In order to make the most appropriate assessment of efficacy for the compound and not be influenced by early dropouts not due to drug the Evaluable set will require at least 4 weeks of RXC004 intake

and at least one post dose radiographic tumour assessment or progressed/died ahead of the first radiographic assessment instead of one single dose as initially planned.

After an ongoing review of the available data the following changes to the final outputs were made compared to the protocol

- Medical History will not be summarized but will be listed.
- CCI [REDACTED]
- Overall Survival will not be summarized but will be listed.

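### SAP 4.2.4 and Protocol 4.5 class a consent withdrawal as study completion, contrary to Protocol 7.2 and 9.4.1.1; applied as written, this overstates the completed count in the disposition table

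*SAP*

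**What the plan says.** SAP 4.2.4 opens with a participant-level rule: "A participant is considered to have completed the study if he/she has completed all phases of the study". After a parenthesis on the last visit and last scheduled assessment, it adds a second route to the same status: "or withdraws consent whichever occurs first". Protocol 4.5 has the same rule. In both documents the end of the study as a whole is defined separately, in the next paragraph.

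SAP 4.4.1 then describes the disposition table. Among other counts, the number of patients "who completed the study or discontinued and primary reason for end of treatment will be summarized" by arm in the FAS. For the accompanying listing it says that "date of first/last intake of study drug and the primary reason for End of Treatment will be listed". Neither output names a reason for leaving the study.

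The protocol commits to more. Section 9.4.1.1 states: "Patient disposition will be presented together with withdrawals from treatments, withdrawals from the study, and the reason for withdrawal". Section 7.2 treats leaving at the participant's own request as withdrawal from the study, and Section 7.1 warns: "Discontinuation from study treatment is NOT the same thing as a withdrawal from the study".

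**The concern.** Disposition tables exist to show who stayed under observation and who did not, and why. A rule that puts consent withdrawals on the completed side makes retention look better than it was, and it contradicts the protocol's own classification.

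It also treats similar losses differently. A patient lost to follow-up (Protocol 7.3) or withdrawn by the investigator (Protocol 7.2) meets neither route to completion. A patient who withdraws consent meets the second.

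What is at stake is the accuracy of one reported count, and whether a reader can find the later withdrawals and their reasons. In arms of this size readers look to disposition when they consider why follow-up of PFS and OS ended, so the count should be right even though no analysis uses it.

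**Working it through.** The documents state no completion rate, so there is no figure to reproduce. The check compares the texts and then scales the effect by simple proportion.

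**Step 1: classify four kinds of patient under each text.**

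| Patient | SAP 4.2.4 and Protocol 4.5, read literally | Protocol 7.2, 7.3 and 9.4.1.1 | Reason named in SAP 4.4.1 |
|---|---|---|---|
| Withdraws consent while on treatment | Completed | Study withdrawal, with reason | End-of-treatment reason, which can show the patient's decision |
| Stops treatment for progression, withdraws consent in survival follow-up | Completed | Study withdrawal, with reason | Progression, as the end-of-treatment reason; nothing for the later withdrawal |
| Withdrawn by the investigator | Not completed | Study withdrawal, with reason | End-of-treatment reason only |
| Lost to follow-up | Not completed | Lost to follow-up | End-of-treatment reason only |

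The first two rows are the conflict. The second is the case in which the SAP outputs alone would give no sign of the withdrawal.

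**Step 2: see whether the SAP departs from the protocol on purpose.** SAP 4.15 says "the following changes to the final outputs were made compared to the protocol" and then lists them. The visible items do not drop the presentation of study withdrawals and reasons. One item is redacted, so this covers only what can be read. On the visible text the protocol commitment still stands, and SAP 4.4.1 does not carry it out in full.

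**Step 3: scale the effect.** Let w be the number of consent withdrawals in an arm and n the number of FAS patients in that arm. The overstatement of the completion rate is w/n. The planned FAS size is redacted. The only visible figure is the target of about 20 evaluable patients per arm (Protocol 9.2, SAP 4.14), used here as an assumed n:

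- w = 1: 1/20 = 5 percentage points
- w = 2: 2/20 = 10 points
- w = 4: 4/20 = 20 points

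SAP 4.15 requires more of an evaluable patient than the single dose that qualifies for the FAS. An arm that reaches its evaluable target could therefore have an FAS above 20. With an assumed n of 25, one withdrawal moves the rate by 1/25 = 4 points. The documents give no expected number of withdrawals.

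**Step 4: look for completer status in the efficacy rules.** DCR and ORR rest on best overall response (SAP 3.2.1.2 and 3.2.1.3). PFS is censored at the last evaluable scan (SAP 3.2.1.5) and OS at the last date known alive (SAP 3.2.1.6). None uses completer status.

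**The case against.** The strongest reply is that the sentence fixes when a participant's time in the study ends. It sits under an end-of-study heading, and its closing words are about timing. SAP 4.4.1 does not cite SAP 4.2.4, and the eCRF on which the SAP is based is not available here, so completion may be recorded in a way that avoids the problem. This has force: the overstatement depends on the rule being applied as written. It does not remove the conflict. The text says completed, the SAP defines that status nowhere else, and SAP 4.4.1 uses the same word as a category set against discontinued. If only timing was meant, the sentence still needs rewording.

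A reader might go further and infer that consent withdrawals will be hidden. The documents do not support that. Protocol 9.4.1.1 requires study withdrawals and reasons to be presented, and a withdrawal during treatment can appear under the end-of-treatment reason. Only withdrawals after treatment are at risk of going unseen, and only if the outputs stop at what SAP 4.4.1 names.

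A reader might also infer that PFS or OS is affected. Their censoring rules do not refer to completion, and both endpoints are listed for every FAS patient (SAP 4.11.3.2 and 4.11.3.3). A completed-or-discontinued count would not by itself show whether censoring was informative; withdrawals with their reasons bear on that more directly.

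Finally, Protocol 7.2 expects withdrawal to be uncommon, so the number of patients concerned may be small.

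**Conclusion.** The point holds as a minor reporting error in a stated rule. SAP 4.2.4 and Protocol 4.5 class consent withdrawal as completion, against Protocol 7.2 and 9.4.1.1. Followed literally, the completed row in the SAP 4.4.1 table is too high by one patient per consent withdrawal, and a withdrawal after treatment has no named place in the SAP outputs.

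The 5-point figure is an illustration that rests on an assumed 20 patients per arm, not an expected effect. The conclusion also assumes that the completed row follows SAP 4.2.4 and that the redacted item in SAP 4.15 does not address study withdrawals. DCR, ORR, PFS and OS are unchanged.

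**What to change.** - **SAP 4.2.4:** remove consent withdrawal from the definition of completion, or relabel the sentence as defining the participant's end of participation, with completion as only one of the ways it can occur.
- **SAP 4.4.1:** count consent withdrawal as study discontinuation, and add study withdrawals with their reasons to both the table and the listing, separately from the end-of-treatment reason.
- **Protocol 4.5:** align the wording at the next amendment. The reporting need can be met in the SAP alone, so this does not justify an amendment of its own.

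The cost is a few lines of SAP text and a change to one disposition table and its listing. No new data item is implied, since Protocol 9.4.1.1 already commits to reporting reasons; the study team should confirm that the eCRF records the reason for leaving the study as well as the reason for stopping treatment.
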